8.5.1 Safety Monitoring Rules for Liver Chemistry Tests

The following rules are adapted from the draft guidance for industry, “Drug-Induced Liver Injury: Premarketing Clinical Evaluation,” issued by the U.S. Department of Health and Human Services, Food and Drug Administration, July 2009.

In the event of an ALT or AST measurement that is $> 3 \times \text{ULN}$ (or the greater of $2 \times$ baseline value or $3 \times \text{ULN}$ if the baseline value was $> \text{ULN}$), at any time during the study (treatment or post-treatment period), the initial measurement(s) should be confirmed as described above. Similarly, confirmatory measurements should also be performed if ALT or AST levels increase to $5 \times \text{ULN}$.

Frequency of Repeat Measurements: Patients with confirmed ALT or AST levels $> 3 \times \text{ULN}$ (or the greater of $2 \times$ baseline value or $3 \times \text{ULN}$ if the baseline value was $> \text{ULN}$), that are continuing to rise should have their liver chemistry tests (ALT, AST, ALP, INR and total bilirubin) retested at least once-weekly until levels stabilize and begin to recover (ALT and AST levels become $\leq 1.2 \times \text{ULN}$ or $1.2 \times$ baseline value if the baseline value was $> \text{ULN}$).

Further Investigation into Liver Chemistry Elevations: For patients with confirmed ALT or AST levels $> 3 \times \text{ULN}$ (or the greater of $2 \times$ baseline value or $3 \times \text{ULN}$ if the baseline value was $> \text{ULN}$), the following evaluations should be performed:

1. Obtain a more detailed history of symptoms and prior and concurrent diseases
2. Obtain further history for concomitant drug use (including nonprescription medications, herbal and dietary supplement preparations), alcohol use, recreational drug use, and special diets
3. Obtain a history for exposure to environmental chemical agents and travel
4. Total, direct and indirect bilirubin
5. Serology for viral hepatitis (HAV IgM, HBsAg, HCV antibody, HCV mRNA, CMV IgM, and EBV antibody panel)
6. Serology for autoimmune hepatitis (e.g., antinuclear antibody [ANA], antismooth muscle antibody, type 1 anti-liver kidney microsomal antibody)
7. Serum acetaminophen-protein adducts by high pressure liquid chromatography if recent acetaminophen usage by patient

Additional liver evaluations, including gastroenterology/hepatology consultations, hepatic CT or MRI scans, may be performed at the discretion of the Investigator, in consultation with the Study Medical Monitor. Repetition of the above evaluations should be considered if a patient’s ALT and/or AST levels reach $5 \times \text{ULN}$.

8.5.2 Safety Monitoring Rules for Renal Function

In the event of a confirmed (as described in Section 8.5) laboratory result meeting 1 or more of the following criteria, urinalysis (see Appendix B) will be required approximately every 2-3 weeks.*

- a. Creatinine clearance by CKD-EPI $< 60 \text{ mL/min/1.73m}^2$
- b. Creatinine clearance by CKD-EPI decrease from baseline** $> 25\%$
- c. Urine Alb/C ratio $> 5 \times \text{ULN}$
- d. Serum creatinine increase from baseline** $> 0.5 \text{ mg/dL}$

* urine collection should be performed at the same time as the protocol specified collection of serum creatinine (see Appendix A)

** baseline is Wk1D1 value

In addition, the first confirmed result meeting a criterion (at any time on study) will trigger an immediate evaluation by a local nephrologist, ideally within 1-week. The following labs should be obtained immediately: fasting serum creatinine, urine culture, 24-hour urine sample for creatinine clearance and urine protein, and urine microscopy sample with nephrologist's inspection of sediment. Consideration of a dose pause (for example with a confirmed CKD-EPI decrease $> 25\%$) should be discussed with the Study Medical Monitor. A mandatory dose pause will occur with a 24-hour urine protein result of $> 2.0 \text{ g}$.

If a patient remains stable over time they may be moved to less frequent monitoring of urinalysis at the discretion of the Study Medical Monitor in consultation with a nephrologist and the Investigator.

If a patient meets a renal monitoring rule that is confirmed on repeat testing, the Investigator should review the patient's concomitant medications for potentially nephrotoxic agents, and carefully consider discontinuing non-essential medications. Consultation with the Study Medical Monitor is encouraged.

8.5.3 Safety Monitoring Rules for Ocular Effects

All patients should receive an ophthalmology examination by an eye specialist at Baseline, after approximately 7 months of receiving Study Drug (Week 29) and also at the end of the dosing period (Week 65). An ERG will also be performed at Baseline and the end of the dosing period (Week 65). In addition, any patient that complains of persistent ocular symptoms compatible with vitamin A deficiency (e.g., night blindness or dry eyes) should be referred for an ophthalmology examination. If the ophthalmologist confirms the patient's symptoms are consistent with vitamin A deficiency and/or the examination reveals physical findings that are consistent with vitamin A deficiency (but do not reach the stopping rule criteria described in Section 8.6.4) then an ERG examination should be conducted and analyzed by the central reader. In addition, it is suggested that a review of diet and supplement use and an evaluation for factors which may contribute to low vitamin A levels such as infection, alcohol consumption, and zinc and/or iron deficiency be conducted.

If the ERG is changed from baseline and shows clear signs of vitamin A deficiency as assessed by the central reader and described below, then the patient should be monitored more frequently. Frequency will be determined by the Sponsor Medical Monitor in consultation with the Investigator and ophthalmologist.

Clear signs of vitamin A deficiency as assessed by ERG include:

- a) Changes from baseline > 50%, and
- b) Values below normal range (if baseline values were within normal range), and
- c) Changes that are approximately symmetrical between eyes (unless there is an alternative explanation for asymmetry)

Dosing with Study Drug may continue while these evaluations are being performed.

8.5.4 Safety Monitoring Rules for Platelet Count Results

Platelets will be monitored weekly throughout the treatment period and for a minimum of 6 weeks after the last dose of Study Drug (this includes early termination patients as well as patients that complete the full 65-week treatment period). For patients participating in the Post-Treatment Evaluation Period, frequency of testing after the Week 71 visit will be determined by the Investigator in consultation with the Study Medical Monitor. For patients participating in the ISIS 420915-CS3 study, weekly monitoring should continue between the last dose of Study Drug in CS2 and first dose of Study Drug in CS3. If this period extends beyond 6 weeks, the frequency of monitoring will be determined by the Study Medical Monitor.

All platelet count results must be promptly reviewed by the Investigator to ensure that the count has not met the stopping rule.

If for any reason there is more than 14 days between platelet values (e.g., lab report of an unreadable sample due to clumping, hemolysis, or quantity not sufficient, or a missed lab assessment), the Investigator will contact the patient to hold dosing until a new platelet value is obtained and reviewed.

If a patient's platelet counts fall below $100,000/\text{mm}^3$, additional lab tests may be requested as determined by the Investigator in consultation with the Study Medical Monitor.

8.6 Stopping Rules

8.6.1 Stopping Rules for Liver Chemistry Elevations

In the event of confirmed laboratory results meeting the following criteria, **and the event is without an alternative explanation as discussed with the Study Medical Monitor**, dosing of a patient with Study Drug (ISIS 420915 or placebo) will be stopped permanently:

1. ALT or AST > 8 x ULN
2. ALT or AST > 5 x ULN at 2 consecutive weekly measurements (not less than 7 days nor more than 10 days apart) both of which are confirmed. Treatment with Study Drug (ISIS 420915 or placebo) may continue until the second consecutive weekly ALT or AST measurement is confirmed to be > 5 x ULN
3. ALT or AST > 3 x ULN **and** total bilirubin > 2 x ULN
4. ALT or AST > 3 x ULN with the appearance of fatigue, nausea, vomiting, right upper quadrant pain or tenderness, fever, rash, and/or concomitant eosinophilia (> 5%)

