8.5 Safety Monitoring Rules

Please refer also to the 'Guidance for Investigator' section of the Investigator's Brochure.

In addition to the standard monitoring of clinical safety parameters, the following guidelines are provided for the monitoring of selected parameters chosen based on preclinical and clinical observations.

Confirmation Guidance: At any time during the study (treatment or post-treatment periods), the initial clinical laboratory results meeting the safety monitoring or stopping criteria presented below **must be confirmed** by performing measurements (ideally in the same laboratory that performed the initial measurement) on new specimens. All new specimen collections should take place as soon as possible (ideally within 3 days of the initial collection).

Stopping Rule Guidance: In the event of an initial clinical laboratory result that meets a stopping criterion, patients must not be re-dosed until a confirmatory test result has been reviewed by the Study Medical Monitor. If any of the stopping criteria described below (refer to Sections 8.6.1 to 8.6.3) are met and are confirmed, the patient will be permanently discontinued from further treatment with Study Drug (ISIS 420915 or placebo), evaluated fully as outlined below and in consultation with the Study Medical Monitor or appropriately qualified designee, and will be entered into the post-treatment evaluation portion of the study (after completing the early termination and EOT efficacy assessments). In general, patients who do not meet the stopping rules based upon retest may continue dosing. However, the Investigator and the Study Medical Monitor (or appropriately qualified designee) should confer as to whether additional close monitoring of the patient is appropriate.

Additional Guidance: If possible, a pharmacokinetic sample should be collected as soon as possible after an SAE has occurred (preferably within 2 weeks). In addition, if a patient is asked to return to the clinic for additional evaluations due to an AE, then a pharmacokinetic sample should be taken at the time of the unscheduled visit.

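### For liver stopping rule 2, Protocol 8.5 prohibits and 8.6.1 permits dosing between a second weekly ALT/AST value above 5 x ULN and its confirmation

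*Protocol*

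**What the plan says.** Protocol 8.5 sets a general hold in its guidance on stopping rules. The trigger is "In the event of an initial clinical laboratory result that meets a stopping criterion", and the instruction is that "patients must not be re-dosed until a confirmatory test result has been reviewed by the Study Medical Monitor". The next sentence, on permanent discontinuation, opens "If any of the stopping criteria described below (refer to Sections 8.6.1 to 8.6.3". The liver rules are therefore among the criteria that 8.5 has in view, and it writes no exception for any of them.

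Protocol 8.6.1 lists four liver criteria under a lead-in that requires confirmed results and no alternative explanation. The second criterion is "ALT or AST > 5 x ULN at 2 consecutive weekly measurements (not less than 7 days nor more than 10 days apart"), with a further condition placed on the two values: "both of which are confirmed". It is the only one of the four with a sentence on dosing in the meantime: treatment "may continue until the second consecutive weekly ALT or AST measurement is confirmed to be" above 5 x ULN.

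Two other provisions fix the timing. For a value that reaches 5 x ULN, Protocol 8.5.1 asks only that "confirmatory measurements should also be performed if ALT or AST levels increase to" that level, and states no hold. On confirmation, Protocol 8.5 says "All new specimen collections should take place as soon as possible (ideally within 3 days of the initial collection"). Dosing is once weekly after Week 1 (Protocol 6.1.2 and 8.1).

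**The concern.** A site whose patient has just returned a second weekly ALT or AST value above 5 x ULN has to decide whether the next injection goes ahead while the retest is pending. Section 8.5 says no and 8.6.1 allows it. The patient has by then had two values above 5 x ULN at least 7 days apart.

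Two things are at stake:

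- **Exposure.** In weeks without a clinic visit, the patient or a caregiver may inject at home (Protocol 8.1), so a hold works only if someone tells them. The platelet rule in 8.5.4 instructs the investigator to contact the patient when dosing must be held for a gap in platelet values. The liver rule has no matching instruction.
- **Records.** Medication errors are documented as protocol deviations (Protocol 9.5.3). SAP 3.2.3 summarizes deviations by category, tabulates reasons for dose pauses and lists missed doses. The same injection could be recorded as compliant at one site and as a deviation at another.

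**Working it through.** No figure in the plan bears on this, so the check sets the texts against a timeline. Day 0 is the collection day of the first value above 5 x ULN.

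1. **Day 0 to the second weekly value (day 7 to 10).** Rule 2 needs two weekly values, so one value alone does not meet it. The 8.5 hold is not triggered under rule 2, 8.5.1 asks only for a confirmatory test, and 8.6.1 allows treatment. The texts agree.
2. **Second value to its confirmation.** The confirmatory specimen is ideally taken within 3 days, so at about day 7 + 3 = 10 to day 10 + 3 = 13. Laboratory turnaround and, under 8.5, Study Medical Monitor review follow. In this interval 8.5 prohibits a dose and 8.6.1 permits one. The texts conflict.
3. **After confirmation.** Both sections lead to permanent stopping, with 8.6.1 adding the condition that there is no alternative explanation. On stopping after confirmation there is no prohibition set against a permission.

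The end of the interval also differs. Section 8.5 releases the hold only after the Study Medical Monitor has reviewed the confirmatory result. Rule 2 refers only to the value being confirmed.

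**Doses at issue.** With one dose every 7 days, an interval shorter than 7 days contains at most one scheduled dose. Protocol 6.1.2 asks for clinic-visit blood samples to be drawn before dosing. If the second sample is drawn on a dosing day and that dose is given before the result is known, the next dose is due 7 days later. A retest specimen taken on day 3 then leaves 7 - 3 = 4 days for turnaround and review before that dose. If the second sample is drawn between dosing days, the next dose comes sooner and is more likely to fall in the interval. The usual range is therefore zero or one dose. More than one becomes possible only if confirmation and review run past a week, which the text does not exclude because the 3 days are only an ideal.

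**Other liver rules.** Rules 1, 3 and 4 have no sentence allowing treatment to continue, so they do not conflict with 8.5.

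**The case against.** The strongest objection is that an unconfirmed second value does not yet meet rule 2. The rule itself demands two values "both of which are confirmed", so the 8.5 hold would not be triggered and the texts would agree. This has some force, because rule 2 is the only liver criterion that repeats the demand within its own wording. But the 8.6.1 lead-in requires confirmed results for all four liver rules, and 8.6.3 requires a confirmed platelet count. On that reading the hold after an initial result would never operate for any liver or platelet rule. It has content only if an initial result meets a criterion when it would do so once confirmed.

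A second objection is that specific text qualifies general text, so rule 2 is a deliberate exception. That is plausible, and it may be what was meant. Neither section says so, and 8.5 is worded as a prohibition. A variant, that the rule 2 sentence covers only the week between the two values, does not fit the words, which run until the second value is confirmed.

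Three limits stand, and each answers a stronger reading that a reader might infer:

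- *That sites have opposite orders.* They do not. A prohibition is set against a permission, and no text requires a dose in this interval.
- *That the conflict covers the whole of rule 2, or all the liver rules.* It covers only the interval after the second value.
- *That sites would count liver-rule stops differently.* This is not supported. Permanent stopping depends on confirmed results under both sections, and SAP 3.9.4 tabulates patients who stopped because they met a rule, not interim holds.

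**Conclusion.** The inconsistency is real but narrow. For liver rule 2, between a second weekly value above 5 x ULN and its confirmation, 8.5 prohibits a dose that 8.6.1 permits, and nothing in the protocol or SAP resolves this. What can vary by site is whether a dose is given in that interval, whether Study Medical Monitor review is awaited, and whether the dose is recorded as a deviation.

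The size is usually zero or one dose per affected patient. This assumes that confirmation and review finish within a week. That few patients would be affected is also an assumption, since the documents give no expected rate of such elevations. No efficacy endpoint, analysis set or error rate is involved. The point is a clarification within a safety rule and does not call the design into question.

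**What to change.** Reconcile 8.5 and 8.6.1 rule 2. State in one place what happens to dosing between the second weekly ALT or AST value above 5 x ULN and its confirmation, and whether Study Medical Monitor review of the confirmatory result is required. Cross-refer from the other section, so that rule 2 is explicitly either an exception to the general hold or subject to it. Which of these applies is for the sponsor's medical team.

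The cost is one sentence in the next amendment or a clarification letter to sites. The SAP needs no change.

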8.6.2 Stopping Rules for Renal Function Test Results

In the event of an estimated creatinine clearance by CKD-EPI meeting any of the following criteria, a serum creatinine and 24-hour urine sample for creatinine clearance and protein should be obtained:

- CKD-EPI decrease of > 50% from baseline
- Value < 45 mL/min/1.73 m² (if baseline CKD-EPI > 60 mL/min/1.73 m²)
- Value < 30 mL/min/1.73 m² (if baseline CKD-EPI ≤ 60 mL/min/1.73 m²)

Dosing of a patient with Study Drug (ISIS 420915 or placebo) will be stopped permanently if the 24-hour urine testing confirms any of the following values in the absence of an alternative explanation agree by a consulting nephrologist:

- urine protein is > 3.5 g
- creatinine clearance < 45 mL/min/1.73 m² (if baseline CKD-EPI > 60 mL/min/1.73 m²)
- creatinine clearance < 30 mL/min/1.73 m² (if baseline CKD-EPI ≤ 60 mL/min/1.73 m²)

Irrespective of whether the stopping rule is confirmed or not, the follow-up schedule and frequency of renal function monitoring after the initial event will be determined by the Study Medical Monitor in consultation with the Investigator and a renal consult will be requested.

8.6.3 Stopping Rule for Platelet Count Results

In the event of a confirmed platelet count less than 75,000/mm³, and in the presence of major bleeding or clinically-relevant non-major bleeding (defined below; Schulman et al. 2005), dosing of a patient with Study Drug (ISIS 420915 or placebo) will be stopped permanently. The follow-up schedule for any events meeting this stopping criterion will be determined by the Investigator in consultation with the Study Medical Monitor.

In the event of a confirmed platelet count less than 75,000/mm³, and in the absence of major bleeding or clinically-relevant non-major bleeding, further dosing of a patient with Study Drug (ISIS 420915 or placebo) must be held until the platelet count returns to at least 100,000/mm³. Weekly platelet monitoring should continue during this period. In addition, the Investigator should give consideration to collecting duplicate platelet samples for study in a local lab in parallel to the central lab if it would provide quicker access to the patients platelet count. If the platelet count was confirmed to be < 50,000/mm³, then monitoring should be increased to daily until two successive values show improvement. The Investigator must notify the Study Medical Monitor within 24 hours of any local lab platelet results that show a level < 50,000/mm³.

The suitability of the patient for continued dosing and the need for any modification to treatment schedule or dose (refer to Section 8.7) will be determined by the Investigator in consultation with the Study Medical Monitor and will be based on factors such as the original rate of decline in the patient's platelet count, whether any bleeding events were experienced by the patient, and the speed of recovery of platelet count upon holding of dosing.

Definition major bleeding events:

International Society on Thrombosis and Haemostasis (ISTH) Major Bleeding:

1. Fatal bleeding, and/or
2. Symptomatic bleeding in a critical area or organ, such as intracranial, intraspinal, intraocular, retroperitoneal, intraarticular or pericardial, or intramuscular with compartment syndrome, and/or
3. Bleeding causing a fall in hemoglobin level of 20 g/L (1.24 mmol/L) or more within 24 hours, or leading to transfusion of 2 or more units of whole blood or red cells

Definition clinically-relevant, non-major bleeding events:

1. Multiple-source bleeding
2. Spontaneous hematoma > 25 cm²
3. Excessive wound hematoma (not injection site related)
4. Macroscopic hematuria (spontaneous or lasting > 24 hours if associated with an intervention)
5. Spontaneous rectal bleeding; epistaxis, gingival bleeding, hemoptysis, hematemesis
6. Bleeding after venipuncture for > 5 minutes

8.6.4 Stopping Rule for Ocular Effects

A patient should be permanently discontinued from Study Drug if an ERG is changed from baseline and shows clear signs of vitamin A deficiency (as described in Section 8.5.3) and an ophthalmology examination reveals significant changes from baseline in any 1 of certain physical signs (Bitot's spots, xerophthalmic ulcers, keratomalacia, or other signs and symptoms of corneal necrosis) and a consultation with the central reader has occurred.

8.6.5 Stopping Rule for QTc Prolongation

In the event of an ECG QTc value (average of triplicates) above the thresholds described below, repeat triplicate ECGs should be performed approximately 1 hour later and further dosing should be discussed with the Study Medical Monitor.

- QTc > 500 msec (if baseline QTc ≤ 470 msec) or
- Increase in QTc value > 60 msec from baseline (all patients)

The suitability of the patient for continued dosing, the need for any modification to treatment schedule or dose (refer to Section 8.7) and the most appropriate follow-up schedule, will be determined by the Investigator in consultation with the Study Medical Monitor. Suitability of continued dosing will be based on factors such as clinical symptoms, width of QRS complex, presence or absence of paced rhythm, and the firing of a defibrillator (in the case that the patient

has an implantable defibrillator). In addition, consideration should be given to an expert cardiology read of the patients' ECGs and a cardiology consult. If a patient is deemed suitable for continued dosing, more frequent ECGs will be performed, with the frequency to be determined by the Investigator and Study Medical Monitor. Any additional monitoring/investigation will also be determined by the Investigator and Study Medical Monitor.

